# 2. Non-target Disease:

- CR: Disappearance of all non-target lesions and normalization of tumor marker levels. All lymph nodes must be 'normal' in size (<10 mm short axis).
- Non-CR/Non-PD: Persistence of any non-target lesions and/or tumor marker level above the normal limits.
- PD: Unequivocal progression of pre-existing lesions. Generally the overall tumor burden must increase sufficiently to merit discontinuation of therapy. In the presence of SD or PR in target disease, progression due to unequivocal increase in non-target disease should be rare

• Indeterminate: Progression has not been determined and one or more non-target sites were not assessed or assessment methods were inconsistent with those used at baseline.

#### 3. New Lesions:

The appearance of any new unequivocal malignant lesion indicates PD. If a new lesion is equivocal, for example due to its small size, continued assessment will clarify the etiology. If repeat assessments confirm the lesion, then progression should be recorded on the date of the initial assessment. A lesion identified in an area not previously scanned will be considered a new lesion.

### 4. Supplemental Investigations:

- If CR determination depends on a residual lesion that decreased in size but did not disappear completely, it is recommended the residual lesion be investigated with biopsy or fine needle aspirate. If no disease is identified, objective status is CR.
- If progression determination depends on a lesion with an increase possibly due to necrosis, the lesion may be investigated with biopsy or fine needle aspirate to clarify status.

# 5. Subjective Progression:

Patients requiring discontinuation of treatment without objective evidence of disease progression should not be reported as PD on tumor assessment CRFs. This should be indicated on the end of treatment CRF as off treatment due to Global Deterioration of Health Status. Every effort should be made to document objective progression even after discontinuation of treatment.

Table 8. Objective	Response Status at	Each Evaluation
--------------------	--------------------	-----------------

Target Lesions	Non-target Disease	New	Objective status
		Lesions	
CR	CR	No	CR
CR	Non-CR/Non-PD	No	PR
CR	Indeterminate or Missing	No	PR
PR	Non-CR/Non-PD, Indeterminate, or Missing	No	PR
SD	Non-CR/Non-PD, Indeterminate, or Missing	No	Stable
Indeterminate or Missing	Non-PD	No	Indeterminate
PD	Any	Yes or No	PD
Any	PD	Yes or No	PD
Any	Any	Yes	PD

If the protocol allows enrollment of patients with only non-target disease, the following table will be used:

# Table 9. Objective Response Status at each Evaluation for Patients with Non Target Disease Only

Non-target Disease	New Lesions	Objective status
CR	No	CR
Non-CR/Non-PD	No	Non-CR/Non-PD
Indeterminate	No	Indeterminate
Unequivocal progression	Yes or No	PD
Any	Yes	PD

# **Appendix 6. Immune-related Response Criteria Derived From RECIST** v1.1 (irRECIST)

Increasing clinical experience indicates that traditional response criteria may not be sufficient to fully characterize activity in this new era of targeted therapies and/or biologics.

This is particularly true for immunotherapeutic agents such as anti-CTLA-4, anti-PD-1 and anti PD-L1 which exert the antitumor activity by augmenting activation and proliferation of T-cells, thus leading to tumor infiltration by T-cells and tumor regression rather than direct cytotoxic effects. Clinical observations of patients with advanced melanoma treated with ipilimumab, for example, suggested that conventional response assessment criteria such as Response Evaluation Criteria in Solid Tumors (RECIST) and WHO criteria are not sufficient to fully characterize patterns of tumor response to immunotherapy because tumors treated with immunotherapeutic agents may show additional response patterns that are not described in these conventional criteria. 87,92

Furthermore, the conventional tumor assessment criteria (RECIST and WHO criteria) have been reported as not capturing the existence of a subset of patients who have an OS similar to those who have experienced CR or PR but were flagged as PD by WHO criteria.

On these grounds, a tumor assessment system has been developed that incorporates these delayed or flare-type responses and designated Immune-related Response Evaluation Criteria In Solid Tumors (irRECIST).

For irRECIST, only target and measurable lesions are taken into account.

In contrast to RECIST 1.1, irRECIST:

- Requires confirmation of both progression and response by imaging at least 4 weeks from the date first documented; and,
- Does not necessarily score the appearance of new lesions as progressive disease if the sum of lesion diameters of target lesions (minimum of 10 mm per lesion, maximum of 5 target lesions, maximum of 2 per organ) and measurable new lesions does not increase by ≥20%.

The same method of assessment and the same technique should be used to characterize each identified and reported target lesion(s) at baseline and throughout the trial.

irRECIST responses are defined as follows:

- Overall immune-related complete response (irCR): Complete disappearance of all lesions (whether measurable or not) and no new lesions. All measurable lymph nodes also must have a reduction in short axis to <10 mm.
- Overall immune-related partial response (irPR): Sum of the longest diameters of target and new measurable lesions decreases ≥30%.

- Overall immune-related stable disease (irSD): Sum of the longest diameters of target and new measurable lesions neither irCR, irPR, (compared to baseline) or immune-related progressive disease (irPD, compared to nadir).
- Overall immune-related progressive disease (irPD): Sum of the longest diameters of target and new measurable lesions increases ≥20% (compared to nadir) with a minimum absolute increase of 5 mm, confirmed by a repeat, consecutive observation at least 4 weeks from the date first documented.

New measurable lesions: Incorporated into tumor burden.

In order to be selected as new measurable lesions ( $\leq 2$  lesions per organ,  $\leq 5$  lesions total, per timepoint), new lesions must meet criteria as defined for baseline target lesion selection and meet the same minimum size requirements of 10 mm in long diameter and minimum 15 mm in short axis for new measurable lymph nodes. New measurable lesions shall be prioritized according to size, and the largest lesions shall be selected as new measured lesions.

All new lesions not selected as new measurable lesions are considered new non-measurable lesions and are followed qualitatively.

New non-measurable lesions: Do not define progression but preclude irCR.

Table 10. Overall Responses derived from Changes in Index, Non-index, and New Lesions

Measurable	Non-Measurable Response		Overall Response
Response Tumor burden a	Non-index lesions	New, non-measurable lesions	using irRECIST b
↓ 100%	Absent	Absent	irCR
↓ 100%	Stable	Any	irPR
↓ 100%	Unequivocal Progression	Any	irPR
↓≥30%	Absent/ stable	Any	irPR
↓≥30%	Unequivocal Progression	Any	irPR
↓ <30% and ↑<20%	Absent/ Stable	Any	irSD
↓ <30% and ↑<20%	Unequivocal Progression	Any	irSD
↑≥20%	Any	Any	irPD

<sup>a Decreases assessed relative to baseline.

<sup>b Response (irCR and irPR) and progression (irPD) must be confirmed by a second, consecutive assessment at least 4 weeks part.

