# 5. Target Lesions:

All measurable lesions up to a maximum of 2 lesions per organ, 5 lesions in total, representative of all involved organs, should be identified as target lesions at baseline. Target lesions should be selected on the basis of size (longest lesions) and suitability for accurate repeated measurements. Record the longest diameter for each lesion, except in the case of pathological lymph nodes for which the short axis should be recorded. The sum of the diameters (longest for non-nodal lesions, short axis for nodal lesions) for all target lesions at baseline will be the basis for comparison to assessments performed on study.

- If two target lesions coalesce the measurement of the coalesced mass is used. If a large target lesion splits, the sum of the parts is used.
- Measurements for target lesions that become small should continue to be recorded. If a target lesion becomes too small to measure, 0 mm should be recorded if the lesion is considered to have disappeared; otherwise a default value of 5 mm should be recorded.

NOTE: When nodal lesions decrease to <10 mm (normal), the actual measurement should still be recorded.

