PR: Partial response is defined (per RECIST 1.1) as at least a 30% decrease in the sum of diameters of target lesions, taking as reference the baseline sum diameters.

SD: At least one objective status of stable or better documented at least 6 (-5 Days) weeks (in consideration of study monitoring schedule) after start date and before progression and the start of new anti-cancer therapy but not qualifying as CR or PR.

PD: Progression documented after start date and not qualifying as CR, PR or SD.

Not Evaluable (NE): All other cases. Note that reasons for NE should be summarized and the following reasons could be used:

- Early death : death prior to 6 weeks after start date
- No post-baseline assessments
- All post-baseline assessments have overall response NE
- New anti-cancer therapy started before first post-baseline assessment
- SD too early (< 6 (-5 days) weeks after start date)

Special and rare cases where BOR is NE due to early SD will be classified as ‘SD too early’.

irRECIST

In addition to the RECIST 1.1, this study is also assessing patients' response using irRECIST criteria.

For irRECIST, with the exception of a complete response assessment, only target and new measurable lesions are taken into account. In contrast to RECIST v1.1, the irRECIST:

Requires confirmation of both progression and response by imaging at least 4 weeks from the date first documented, and

Does not necessarily score the appearance of new lesions as progressive disease if the sum of lesion diameters of target lesions (maximum of 5 target lesions, maximum of 2 per organ) and measurable new lesions does not increase by $\geq 20\%$.

The same method of assessment and the same technique should be used to characterize each identified and reported target lesion(s) at baseline and throughout the study.

irRECIST responses are defined as follows:

- **Overall immune-related complete response (irCR):** Complete disappearance of all lesions (whether measurable or not) and no new lesions. All measurable lymph nodes also must have a reduction in short axis to <10 mm.
- **Overall immune-related partial response (irPR):** Sum of the diameters (longest for non-nodal lesions, shortest for nodal lesions) of target and new measurable lesions decreases $\geq 30\%$.

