- **Overall immune-related stable disease (irSD):** Sum of the diameters (longest for non-nodal lesions, shortest for nodal lesions) of target and new measurable lesions does not meet criteria for irCR or irPR, (compared to baseline) or immune-related progressive disease (irPD, compared to nadir).

- **Overall immune-related progressive disease (irPD):** Sum of the diameters (longest for non-nodal lesions, shortest for nodal lesions) of target and new measurable lesions increases $\geq 20\%$ (compared to nadir) with a minimum absolute increase of 5 mm, confirmed by a repeat, consecutive observation at least 4 weeks from the date first documented.

New measurable lesions: Incorporated into tumor burden (ie, added to the target lesion measurements). In order to be selected as new measurable lesions (≤ 2 lesions per organ, ≤ 5 lesions total, per timepoint), new lesions must meet criteria as defined for baseline target lesion selection and meet the same minimum size requirements of 10 mm in long diameter and minimum 15 mm in short axis for new measurable lymph nodes. New measurable lesions shall be prioritized according to size, and the largest lesions shall be selected as new measured lesions.

New non-measurable lesions: Do not define progression but preclude irCR.

Table 2. Overall Responses Derived from Changes in Target, Non-target, and New Lesions

Measurable disease	Non-measurable disease		
Target and New Measurable Lesions (Tumor Burden) ^a	Non-Target Lesions	New, non-measurable Lesions	Overall response using irRECIST ^b
Decrease 100%	Absent	Absent	irCR
Decrease 100%	Stable	Any	irPR
Decrease 100%	Unequivocal progression	Any	irPR
Decrease $\geq 30\%$	Absent/stable	Any	irPR
Decrease $\geq 30\%$	Unequivocal progression	Any	irPR
Decrease $< 30\%$ and increase $< 20\%$	Absent/stable	Any	irSD
Decrease $< 30\%$ and increase $< 20\%$	Unequivocal progression	Any	irSD
Increase $\geq 20\%$	Any	Any	irPD

^a Decreases assessed relative to baseline

^b Response (irCR and irPR) and progression (irPD) must be confirmed by a second, consecutive assessment at least 4 weeks apart.

Derivation of BOR and irBOR

Examples of objective status sequences and overall response for a tumor assessment interval of at least 4 weeks and at least as long as the minimum assessment time to qualify as SD are shown in [Table 3](#). This will vary for other assessment schedules.

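### The protocol's irRECIST appendix sums longest diameters for every lesion while the SAP uses short axis for lymph nodes, and both irCR table rows omit the nodal rule in their own text, so some patients with nodal lesions can be classified inconsistently.

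*Protocol*

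**What the plan says.** **Nodal measure.** Protocol Appendix 6 defines irPR as "Sum of the longest diameters of target and new measurable lesions decreases ≥30" percent and irPD as "Sum of the longest diameters of target and new measurable lesions increases ≥20% (compared to nadir) with a minimum absolute increase of 5 mm"; irSD is worded on the same sum. None of the three mentions nodes. SAP Section 5.8 defines irPR on "Sum of the diameters (longest for non-nodal lesions, shortest for nodal lesions) of target and new measurable lesions decreases" and irPD on "Sum of the diameters (longest for non-nodal lesions, shortest for nodal lesions) of target and new measurable lesions increases", with irSD to match. Elsewhere the protocol treats nodes by short axis: Appendix 5 (A.1 and A.5) measures, records and sums target nodes that way, and Appendix 6 itself uses short axis to decide whether a new node is measurable.

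**irCR.** The text of both documents requires lesions to disappear and adds, in the same words, "All measurable lymph nodes also must have a reduction in short axis to <10 mm". The irCR row of protocol Table 10 reads "100% Absent Absent irCR" and that of SAP Table 2 reads "Decrease 100% Absent Absent irCR"; in both, the 100% refers to the fall in tumour burden. On recording, Appendix 5 (A.5) notes: "When nodal lesions decrease to <10 mm (normal), the actual measurement should still be recorded". The same section records a lesion judged to have disappeared as 0 mm.

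**Use.** Objective response by irRECIST is a secondary endpoint in all four parts. SAP Section 5.8 derives disease control, duration of response, duration of stable disease, PFS and TTP under irRECIST as well as RECIST 1.1. Protocol Sections 5.4.6, 6.4 and 7.4 send sites to Appendix 6 for confirming progression, for withdrawal and for response.

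**The concern.** Two separate inconsistencies meet in one endpoint.

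The first is between the documents. Long and short axes of a node need not change in proportion, so a sum of longest diameters and a sum using nodal short axes are different quantities held against the same 30% and 20% thresholds. A site following Appendix 6 literally and a programmer following the SAP can reach different categories from one set of scans. That can move irRECIST ORR, PFS, TTP and duration of response, and can leave a site-assessed irPD date at odds with the derived one.

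The second is inside each document. The irCR text tolerates a small residual node; the table that assigns the category does not. A patient who is irCR by the text may be something else by the table.

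**Working it through.** The plan states no figure here to reproduce. I applied its category rules to lesion sizes that are my assumption, chosen only to show what the rules can do. Nodes are given as long × short axis in mm, and confirmation is taken as met.

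Rules used, from Appendix 6 and SAP Section 5.8:
- percent fall = (baseline sum − current sum) / baseline sum; irPR at 30% or more;
- percent rise = (current sum − nadir sum) / nadir sum; irPD at 20% or more with at least 5 mm;
- irCR by table at a 100% fall with no non-target or new lesions; otherwise irSD.

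**1. Nodal measure**

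| Case | All longest diameters (Appendix 6) | Short axis for nodes (SAP) |
|---|---|---|
| Response: node 24×16 to 22×8, other lesion 30 to 24 | (54 − 46)/54 = 14.8% fall: irSD | (46 − 32)/46 = 30.4% fall: irPR |
| Progression from nadir: node 22×10 to 26×18, other lesion 20 unchanged | (46 − 42)/42 = 9.5% rise, 4 mm: not irPD | (38 − 30)/30 = 26.7% rise, 8 mm: irPD |
| Check, node only: 24×15 to 14×9 | (24 − 14)/24 = 41.7% fall: irPR by sum | (15 − 9)/15 = 40.0% fall: irPR by sum |
| Check, no nodes: liver 40 to 26 | (40 − 26)/40 = 35.0% fall: irPR | 35.0% fall: irPR |

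The first two rows show that the category can change in either direction of tumour change. The last two show that it need not change with nodes, and does not change without them.

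**2. irCR, text against table**

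| Case, no other disease | Text | Table 10, longest diameters | SAP Table 2, short axis |
|---|---|---|---|
| Liver 30 to 0, node 24×18 to 14×8 | irCR | (54 − 14)/54 = 74.1%: irPR | (48 − 8)/48 = 83.3%: irPR |
| Node only, 25×15 to 20×9 | irCR | (25 − 20)/25 = 20.0%: irSD | (15 − 9)/15 = 40.0%: irPR |
| Liver 30 to 0, node 24×18 judged gone (0 mm) | irCR | 100%: irCR | 100%: irCR |

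I read the text as granting irCR to a node under 10 mm short axis. Otherwise its nodal sentence would have no work to do, and Appendix 5 (B.1) makes that exception openly for RECIST CR.

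**3. Bound for the SAP table.** A target node starts at 15 mm short axis or more. To meet the irCR text it ends below 10 mm, a fall of more than (15 − 10)/15 = 33.3%. Non-nodal lesions fall by 100% and new lesions are not allowed. The SAP sum therefore always falls by more than 33.3%, so SAP Table 2 gives at worst irPR to a patient who meets the irCR text. irSD arises only under longest-diameter summing.

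**4. Does aligning the measure cure both?** No. With short axis in both documents, the first two cases in step 1 agree. The liver-plus-node case in step 2 remains irPR by table and irCR by text.

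**The case against.** The best reply is that Appendix 6 is only loosely worded. It derives from RECIST 1.1, asks for the same assessment method throughout, and uses short axis for irCR and for new nodes. Appendix 5 has sites record the short axis of target nodes, and no instruction to record a node's long axis was found, so the literal sum cannot be formed from the data specified. On this view the SAP makes the intent explicit, and SAP Section 2 says that it supersedes the protocol's statistical considerations.

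Much of this stands. It makes short axis the natural choice for the derived endpoints and limits how often practice will diverge. It does not remove the conflict. SAP precedence covers the analysis, not a site reading Appendix 6. SAP Section 2 also promises to identify substantial differences from the protocol, and the available SAP text does not identify this one.

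Several stronger readings do not hold:
- A reader might infer that irCR is out of reach for anyone with a nodal target lesion. A node judged to have disappeared is recorded as 0 mm, and the sum can reach zero.
- A reader might infer that the irCR row creates a protocol-SAP difference or lowers the response rate. The row is the same in both documents, and under SAP summing the patient moves from irCR to irPR, which both count as response.
- A reader might infer that either table can return irSD for an irCR patient. The 33.3% bound rules that out for the SAP.
- A reader might infer that irPD mechanically ends treatment. Protocol Section 5.4.6 says that patients with confirmed PD should be considered for discontinuation and lets some continue after discussion with the sponsor.

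**Conclusion.** Both inconsistencies are real and should be corrected. The nodal-measure conflict is the more consequential: it can move a patient between irSD and irPR or between irSD and irPD, and so can alter irRECIST ORR, PFS, TTP and duration of response. The irCR conflict costs SAP-derived results only the split between irCR and irPR; under a literal Table 10 it can also cost a response.

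The reach is limited. Only patients with nodal target or new measurable nodal lesions are exposed, and not all of them change category. The documents give no frequency for such lesions, so the number affected cannot be estimated, and the percentages above rest on assumed sizes. It would go too far to say that site and SAP results will disagree; they can. The affected endpoints are secondary and summarised descriptively. DLT and MTD rules, sample size and RECIST 1.1 results are untouched.

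**What to change.** 1. **Nodal measure.** Use one nodal measure for irPR, irSD and irPD in both documents, reconciling Appendix 6 with Appendix 5 and the SAP. For the derived endpoints this is the SAP's rule: longest diameter for non-nodal lesions, short axis for nodes. Because irPD also bears on treatment continuation, the sponsor must reconcile the site-facing passages; this review does not say which rule should govern treatment.
2. **Response tables.** In protocol Table 10 and SAP Table 2, replace the 100% entries with a condition that all non-nodal target and new measurable lesions are absent and all nodal lesions are below 10 mm short axis.
3. **Precedence.** State that these rows are applied before the rows for a decrease of 30% or more. Otherwise a patient with, say, an 83.3% fall and a normalised node fits both an irCR row and an irPR row.

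The cost is wording in Appendix 6, Table 10 and SAP Section 5.8 with Table 2. The derived endpoints need no new measurement, since Appendix 5 already has nodal short axes recorded.

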FFPE	formalin-fixed paraffin-embedded
FIP	first in patient
FSH	follicle-stimulating hormone
GCP	good clinical practice
GITR	glucocorticoid-induced tumor necrosis factor receptor
Gp100	glycoprotein 100
HBV	hepatitis b virus
hCG	human chorionic gonadotropin
HCV	hepatitis c virus
Hgb	hemoglobin
HIV	human immunodeficiency virus
HLA	human leukocyte antigen
HR	heart rate
IB	investigator's brochure
ICD	informed consent document
ICH	international conference on harmonization
ICOS	inducible t-cell co-stimulator
IEC	institutional ethics committee
ID	identification
IFN γ	interferon gamma
IgG	immunoglobulin g
IHC	immunohistochemistry
IL-	interleukin
IM	immunomodulatory
IND	investigational new drug application
INR	international normalized ratio
IRB	institutional review board
IUD	intrauterine device
IV	intravenous
KLH	keyhole limpet hemocyanin
LAG3	lymphocyte-activation gene 3
LFT	liver function test
LPD	local product document
LSLV	last subject last visit
mTPI	modified toxicity probability interval
mAb	monoclonal antibody
MD	multiple dose
MedDRA	medical dictionary for regulatory activities
MRI	magnetic resonance imaging
MTD	maximum tolerated dose
N/A	not applicable
NCI	National Cancer Institute
NF- κ B	nuclear factor kappa-light-chain-enhancer of activated B cells
OBD	optimal biological dose
ORR	objective response rate
OS	overall survival
pT	target probability
PBMCs	peripheral blood mononuclear cells
PCD	primary completion date

Abbreviation	Term
PDs	pharmacodynamics
PD	progressive disease
PD-1	programmed cell death-1
PD-L1	programmed death-ligand 1
PE	physical exam
PET	positron emission tomography
PFS	progression free survival
PK	pharmacokinetics
PLTS	platelets
PR	partial response
PS	performance status
PT	prothrombin time
SAE	serious adverse event
SAP	statistical analysis plan
SC	subcutaneous
SD	stable disease
SDo	Single Dose
SPC	summary of product characteristics
SRSD	single reference safety document
T	time
T1/2	terminal elimination half-life
TBNK assay	TBNK lymphocyte assay
TCR	T-cell receptor
Th	T-helper
TILs	tumor infiltrating lymphocytes
TNF	tumor-necrosis factor
TNF- α	tumor-necrosis factor alpha
TNFR	tumor-necrosis factor receptor
TNFSF4	tumor necrosis factor (ligand) superfamily,member 4
Tregs	T regulatory cells
TPP	time to progression
ULN	upper limit of normal
UPM	unit probability mass
US	United States
USPI	United States package insert
VEGF	Vascular Endothelial Growth Factor
Vss	Volume of distribution at steady state
WBC	White blood cell count

